Despite the substantial burden of chlamydia and adverse pregnancy outcomes, no previous research has been conducted to examine the effects of genital chlamydia infection on adverse pregnancy outcomes in China. There is no clinical guideline on screening for genital Chlamydia infections in pregnant women. Therefore, it is important to understand the impact of genital Chlamydia in China through randomized controlled studies that explore the relationships between Chlamydial infection and adverse pregnancy outcomes, and the feasibility and effectiveness of screening and treatment. The purpose of this study is to 1.) clarify the causal relationship between genital *C. trachomatis* infection and adverse pregnancy outcomes and 2.) determine whether screening and treatment of genital *C. trachomatis* in pregnant women can reduce adverse pregnancy outcomes. The research team will screen pregnant women in Guangzhou for genital *C. trachomatis* to understand its prevalence. We will also conduct a randomized controlled trial to explore whether clinical treatment of *C. trachomatis*-positive patients can reduce adverse pregnancy outcomes, and neonatal chlamydial conjunctivitis and pneumonia. This study will have great scientific and social significance. Firstly, it will provide

an important reference for the formulation of public health policies, clinicians' treatment of chlamydia infection in pregnant women, and prevention of chlamydial infection in newborns. Secondly, it will be a valuable resource for the prevention of adverse pregnancy outcomes and neonatal infection associated with sexually transmitted diseases in other developing countries.

II. Purpose

1. To examine whether screening and treatment of genital C. trachomatis in pregnant women can reduce adverse pregnancy outcomes
2. To explore the effectiveness of screening and treatment of genital C. trachomatis in reducing mother-to-child transmission
3. To evaluate the cost-effectiveness of screening and treating chlamydial infections in pregnant women, and provide a basis for health policy decisions on how best to screen / treat

III. Hypotheses

1. Effective screening and treatment of pregnant women with genital C. trachomatis will reduce adverse pregnancy outcomes
2. Effective screening and treatment of pregnant women with genital C. trachomatis will reduce neonatal chlamydial conjunctivitis and pneumonia
3. C. trachomatis screening and treatment of pregnant women is cost-effective.

IV. Content

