We will adopt the block randomization approach. Specific randomization steps include: 1) After we recruit participants, we will group them into blocks on a chronological basis. Each block will have 20 women who will be numbered sequentially. 2) We will then randomly divide them in each block into intervention and control groups. That is numbering the participants from 1 to 20, then generating 10 random numbers and the corresponding participants will be assigned to the intervention group. For participants in the intervention group, we will immediately test for *C. trachomatis* and *Neisseria gonorrhoeae* (See Figure 1 for the flowchart of the study design). Participants who test positive for either infection in the intervention group will be linked to physicians at the Center for treatment. For the control group, urine samples will be collected and tested immediately after childbirth or in the event of an adverse pregnancy outcome. In the event of a positive test result, the participant will be suggested to return to the Center for further treatment.

[figure not shown]

Figure 1, Flow Chart of the study.

Intervention and Treatment

This RCT will follow the principle of nonmaleficence. For pregnant women enrolled in the intervention group, after completing the test, laboratory personnel will inform the researchers of positive results. The sample number of the positive result will then be reported to the Guangzhou Women and Children Medical Center (GWCMC). The center's physicians will match the result to the correct patient and notify them of their results. We will provide a training session to the physicians at the Center about the national standard treatment plan (Azithromycin 1g, single oral administration). They will be suggested to treat patients according to the Chinese clinical and

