If there is no confirmed diagnosis, family of the newborn will be advised to pay close attention for the emergence of signs of conjunctivitis and / or pneumonia, and promptly return to the hospital if the post-neonatal clinical symptoms appear. This study will follow the treatment guidelines for of the American Academy of Pediatrics Infectious Diseases and America Centers for Disease Control and Prevention for conjunctivitis and pneumonia: Erythromycin 12.5 mg/kg, oral, 4 times a day, for 14 days. For patients that do not return to the hospital for screening, the research team will call patients and verify the newborn infection status and whether treatment was provided at a different hospital.

Justifications of the control strategy

Currently in China, there are no clinical guidelines or policies that suggest routine genital chlamydia screening in pregnant women.¹⁵ The clinical standards for conducting a chlamydia test in pregnant women include relevant symptoms including urethritis, cervicitis and occurrence of adverse pregnant outcomes.¹⁵ Compared to current standard care (i.e., no routine screening and treatment), both our intervention (free screening for chlamydia at recruitment and linkage to care) and control (free screening for chlamydia at delivery of the baby and linkage to care) strategies provide better care to the target group.

Safety management plan

Criteria for withdrawal: if participants want to quit the study for any reasons; occurrence of any adverse pregnancy outcomes or recommendation by their personal physician to stop participation; Data and safety monitoring will be done by The Center and the Dermatology Hospital of Southern Medical University.

In addition, the study complies with the following statements: Any risk is the least possible for achieving the objectives of the research; Each individual providing consent is fully informed regarding the reasonably foreseeable impact of the research on the fetus or neonate; No inducements, monetary or otherwise, will be offered to terminate a pregnancy; Individuals engaged in the research will have no part in any decisions as to the timing, method, or procedures used to terminate a pregnancy; and Individuals engaged in the research will have no part in determining the viability of a neonate.

Primary Outcome

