Our primary outcome is the occurrence of adverse pregnancy-related outcomes between the two groups, which include: 1) stillbirth (the definition of stillbirth in this study will use International Classification of Diseases (ICD-11): death prior to complete expulsion (pregnant ≥ 28 weeks) and death during extraction [17]); 2) Spontaneous abortion (less than 1000gms or less than 28 weeks); 3) Preterm labor (birth fewer than 37 weeks gestational age; Infants born before 28 weeks are considered very early-preterm; 28-32 weeks early-preterm; 32-37 weeks late-preterm. 4) Premature rupture of membranes (prior to onset of labor); 5) Low birth weight (2,499g or less); 6) Small for gestational age (weight below the 10th percentile); and 7) perinatal death.

Secondary Outcomes

The secondary outcomes include: C. trachomatis infection of the newborn, Chlamydial conjunctivitis, and pneumonia in the newborn. Laboratory methods for the diagnosis of neonatal

chlamydial infection include: 1) Detection of *C. trachomatis* by sampling from conjunctival scraps and nasopharyngeal/ pharyngeal posterior through direct fluorescence (DFA); 2) PCR and 3) chlamydia culture.

Common Chlamydia conjunctivitis clinical symptoms and supplementary examinations include eyelid and nasal congestion, or 2) catarrhal or mucopurulent secretions, occurring within 5-14 days after birth. It is possible for exudate adhesions to form pseudomembranes. If treatment is delayed more than two weeks, conjunctival follicles may also form.

Chlamydia pneumonia infection may appear insidiously. However, symptoms will usually appear in 4-12 weeks. Common clinical manifestations include nasal mucus secretion, nasal congestion, intermittent cough, shortness of breath, rales on auscultation. There is usually no fever or change in consciousness. Laboratory examinations may show normal white count but elevated eosinophils; moderate hypoxemia on arterial blood gas; bilateral interstitial markings on chest radiography.

Clinical Data Collection

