Maternal: 1) mode of delivery: vaginal delivery or caesarean section; 2) whether twins or not; 3) occurrence of complications of childbirth, such as fetal umbilical cord around the neck, dystocia, uterine rupture and amniotic fluid embolism; 4) occurrence of stillbirth, spontaneous abortion, or premature rupture of membranes; 5) development of fetus during prenatal period (occurrence of fetal malformations and types of malformations etc.); 6) history of chronic diseases during pregnancy, including gestational diabetes, hypertension, autoimmune diseases, etc.; 7) nutritional status of pregnant woman; 8) HIV and Syphilis test and treatment information for positive cases;

9) essential clinical data: chlamydia and gonorrhea test and treatment information; 10) other clinical information: general health information (height, weight, blood pressure, blood glucose, complete blood count, urine analysis).

Neonatal: 1) Information on birth weight, neonatal death etc.; 2) occurrence of any symptoms such as conjunctivitis, pneumonia, genital infections etc.

Urine collection and laboratory testing

1) Sample collection for pregnant women with Chlamydia trachomatis / gonococcal: We will collect urine samples for testing. Before collection, we will ensure that the patient has not urinated within the last 1 hour. The patient also should not clean the sampling site in advance, such as washing etc. Patients will be instructed to collect urine in a urine cup. Urine in the urine cup cannot remain at room temperature (2-30°C) longer than 24 hours. We will use flexible pipes from the Roche cobas® PCR Urine Sample Kit, to transfer urine to the storage tube (Roche cobas® PCR Media tube). After tightening the lid, storage tubes will be turned over up and down five times. Samples will be transferred to the Dermatology Hospital of Southern Medical University for testing.

2) Neonatal samples collection: We will collect eyelid swabs (sample needs to contain eyelid epithelial cells) and pharyngeal swabs. Samples will be maintained at 2-8°C and screened within 24 hours.

3) Chlamydia trachomatis / Neisseria gonorrhoeae test: Reagent: Roche Cobas CT / NG Test kit; Instrument: Roche Cobas Z480, Roche Cobas X4800. Detection principle: CT: detecting Chlamydia MOMP gene by FAM labeling probe; NG: detecting Neisseria gonorrhoeae DR-9

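### The intervention arm is screened and linked to treatment for gonorrhoea as well as chlamydia, but the aims, hypotheses and description of the intervention name chlamydia only

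*Combined protocol and SAP*

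**What the plan says.** **What differs between the arms.** Participant recruitment and randomization has intervention women tested at once for both organisms, and "Participants who test positive for either infection in the intervention group will be linked to physicians at the Center for treatment". For the other arm: "For the control group, urine samples will be collected and tested immediately after childbirth or in the event of an adverse pregnancy outcome". During pregnancy, then, the randomised groups differ in study screening and linkage to treatment for two infections.

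**What the trial says it studies.** The background section, just before II. Purpose, sets out to "clarify the causal relationship between genital *C. trachomatis* infection and adverse pregnancy outcomes". The first hypothesis reads "Effective screening and treatment of pregnant women with genital C. trachomatis will reduce adverse pregnancy outcomes". All three purposes and all three hypotheses concern chlamydia. Sample size estimation uses a chlamydia prevalence and a chlamydia odds ratio. Justifications of the control strategy describes "our intervention (free screening for chlamydia at recruitment and linkage to care", with no mention of gonorrhoea, and the Annual Plan lists only CT detection and CT treatment.

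**What is measured.** "Our primary outcome is the occurrence of adverse pregnancy-related outcomes between the two groups". It has seven components, from stillbirth to perinatal death, and none is tied to an organism. Clinical Data Collection lists "essential clinical data: chlamydia and gonorrhea test and treatment information", but no analysis of the gonorrhoea data is described.

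**The concern.** The randomised contrast and the stated conclusion do not cover the same thing. A between-arm difference in a general composite of adverse pregnancy outcomes can arise from treating either infection. Under the plan's wording, the whole difference would be reported as the effect of chlamydia screening and treatment.

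This matters because the background section presents the trial as a reference for public health policy and as evidence on chlamydia's causal role. A health authority that introduced a chlamydia-only screen would not be introducing the strategy that was randomised. The cost-effectiveness purpose is exposed in the same way. Nowhere does the plan define the intervention as joint screening, or exclude, stratify by or adjust for gonorrhoea. V. Pilot Study mentions infectious confounders only as something the pilot will look at.

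**Working it through.** **The plan's own figure.** The plan has no gonorrhoea figure to reproduce. Its sample size is built from chlamydia-positive women: 757 / (0.05 × 0.98) = 15,449, which matches the table and contains no gonorrhoea term. The 757 itself does not follow from the stated inputs (an odds ratio of 1.8 on 10%, two-sided 5%, 80% power and 1:1 allocation give 814), and 15,449 sits in the 5% prevalence column while the text says 6%. Neither matter decides this point.

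**Inputs from the plan (Sample size estimation).** Adverse outcome risk 10%; odds ratio 1.8 for chlamydia; chlamydia prevalence 6% (text); 7,725 women per arm; 2% loss.

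**Assumptions, not in the plan.** Gonorrhoea-only prevalence g of 0.1%, 0.5% or 1%; gonorrhoea odds ratio 1.0, 1.8 or 3.0; treatment removes all the excess risk; all randomised women are compared.

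**Step 1: excess risk per infected woman.**
- Odds at 10% risk: 0.10/0.90 = 0.1111.
- Odds ratio 1.8: 0.1111 × 1.8 = 0.200; risk 0.200/1.200 = 16.67%; excess 6.67 percentage points.
- Odds ratio 3.0: 0.1111 × 3.0 = 0.333; risk 0.333/1.333 = 25%; excess 15 points.

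**Step 2: chlamydia's contribution to the arm difference.** 0.06 × 6.67 = 0.40 points.

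**Step 3: standard error of the difference.** Women per arm: 7,725 × 0.98 ≈ 7,570. SE = √(2 × 0.10 × 0.90 / 7,570) = 0.0049, or about 0.49 points.

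**Step 4: gonorrhoea's contribution.** Added difference = g × excess risk. Share = added / (0.40 + added).

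| g (assumed) | Intervention women, 7,725 × g | Added, OR 1.8 (points) | Share, OR 1.8 | Added / SE, OR 1.8 | Share, OR 3.0 |
|---|---|---|---|---|---|
| 0.1% | 8 | 0.007 | 1.6% | 0.01 | 3.6% |
| 0.5% | 39 | 0.033 | 7.7% | 0.07 | 15.8% |
| 1% | 77 | 0.067 | 14.3% | 0.14 | 27.3% |

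With odds ratio 1.0 every share is zero. When both infections have the same odds ratio, the share is simply g / (0.06 + g); with chlamydia at 5% it becomes 2.0%, 9.1% and 16.7%. At odds ratio 3.0 and g = 1% the added difference is 0.15 points, or 0.31 SE. An extreme corner, g = 2% with odds ratio 3.0, gives 0.30 / 0.70 = 43%.

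**Step 5: effect on the test.** Suppose chlamydia treatment had no effect. The chance of a significant result favouring the intervention is Φ(added/SE − 1.96). At odds ratio 1.8 it is 2.9% for g = 0.5% and 3.4% for g = 1%, against 2.5% with no gonorrhoea effect.

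**Step 6: which women are compared.** The background section speaks of treating chlamydia-positive patients, and the sample size table counts positive samples. Primary Outcome and the sample size text speak of the two groups. If only chlamydia-positive women are analysed, gonorrhoea-only women drop out and the table above does not apply; only co-infection remains, for which the plan gives no figure.

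**The case against.** The strongest reply is that the comparison remains a valid randomised one and that gonorrhoea is probably a minor contributor. Both parts largely stand. The contrast is a sound estimate of joint screening; only the label and the causal statement are in question. On the assumed 0.1% to 1% with odds ratio 1.8, the added difference is at most 0.14 of a standard error. Still, chlamydia's own assumed contribution, 0.40 points, is also below one standard error. The comparison with the standard error therefore shows that the significance test is hardly affected, not that the label is right.

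A reader might infer more than the documents support:

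- **That the primary outcome itself is credited to chlamydia.** It is not. The definition names no organism; the attribution sits in the aims, purposes, hypotheses and description of the intervention.
- **That women with both infections receive two separate treatments.** Intervention and Treatment names one regimen and otherwise refers to national guidelines and the decision of physician and patient. Retesting and partner treatment are written for chlamydia. For gonorrhoea, the text goes no further than linkage to physicians and that general reference. The either-infection rule and the chlamydia-only follow-up need reconciling, but a second treatment is not stated.
- **That the newborn outcomes are compromised in the same way.** Secondary Outcomes lists laboratory methods for diagnosing neonatal chlamydial infection. Whether a positive result is required is a separate clarification.

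Figure 1, the flow chart, is not shown in the text available, so it cannot be used to settle the definition of the intervention.

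**Conclusion.** The mismatch is real and should be corrected: the plan randomises screening and linkage to treatment for two infections and states its conclusion for one. The size is unknown from the documents. In an all-randomised comparison, with gonorrhoea-only prevalence of 0.1% to 1%, odds ratio 1.8, chlamydia at 6% and full reversal of risk by treatment, gonorrhoea would supply about 2% to 14% of the arm difference. The share is zero if gonorrhoea has no effect on these outcomes, and larger if its odds ratio is higher. In an analysis of chlamydia-positive women only co-infection would matter.

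It would go too far to say that the comparison fails to measure chlamydia screening at all, or that a positive result would be due to gonorrhoea. Across most of the assumed range chlamydia accounts for the bulk of the difference. What the plan cannot do, as written, is show that.

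**What to change.** 1. State the randomised intervention and the primary conclusion as combined C. trachomatis / N. gonorrhoeae screening and linkage to treatment.
2. Reconcile the background aim, II. Purpose, III. Hypotheses, Participant recruitment and randomization, Intervention and Treatment, and Justifications of the control strategy so that they describe the same intervention. State whether the primary comparison takes in all randomised women or chlamydia-positive women only.
3. Confirm that control samples are also read for gonorrhoea. The text says only that they are tested; the CT/NG kit described under Urine collection and laboratory testing suggests that they are.
4. Report gonorrhoea-only and co-infected counts, and the treatment given, by arm.
5. Label any analysis that leaves out gonorrhoea-positive women as exploratory. State its limitation: status is measured at enrolment in one arm and at delivery or an adverse outcome in the other, so the exclusion is not protected by randomisation and in controls can be triggered by the outcome itself.

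The cost is wording, one confirmation from the laboratory and a table from data already due to be collected. The downside is a slightly broader intervention label. No change to clinical care is proposed.

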Target population and sampling

This study will recruit pregnant women from a maternal/child health hospital in Guangzhou city and county. Guangzhou Women and Children Medical Center and Zengcheng Maternal and

Child Health Hospital (now Zengcheng Hospital of Guangzhou Women and Children Medical Center) are two key hospitals for perinatal health and pregnant women. In 2016, Guangzhou Women and Children Medical Center delivered 22,455 infants, the highest delivery volume among the hospitals throughout the city. Additionally, Zengcheng Hospital of Guangzhou Women and Children Medical Center provides prenatal care, delivery care, and other main medical services for pregnant women in Zengcheng district. Given the rich clinical research resources and experience of both hospitals, we have elected to conduct our large-scale randomized controlled clinical trial at these two hospitals.

Inclusion criteria: 1) pregnant women on their first visit to the hospital (regardless of gestational age); 2) aged 18 or above; 3) agree to participate and sign an informed consent. Exclusion criteria: 1) systemic or topical vaginal antibiotics were used within 2 weeks prior to the first perinatal visit; 2) diagnosed adverse pregnancy outcomes at recruitment (e.g., stillbirth); 3) pregnant women who refuse to participate in this study.

Sample size estimation

The sample size calculation was based on the following assumptions: 1, the conservative estimate of prevalence of Chlamydia is around 6% among pregnant women in Guangzhou; 2, our meta-analysis showed that the odd ratio of adverse pregnancy outcomes in infected pregnant women versus non-infected pregnant women was 1.8; 3), assuming a 5% significance level on both sides, with a 80% efficacy test and a 2% loss- to-follow-up rate, in order to demonstrate a significantly lower incidence of adverse pregnancy outcomes in the intervention group than in the control group (estimated at 10%, from preliminary data, unpublished results), the sample size

should be approximately 7,725 for each group with an overall target sample size of 15,450 (when $\beta = 0.8$, the estimated sample size is 15,449).

Alpha	OR	p^2	Power	# of positive samples	Prevalence (%)			Total sample size (include 2% loss-to-follow-up)		
					5	6	8	20,306	16,922	12,691
0.05	1.8	0. 1	0.9	995						
0.05	1.8	0. 1	0.8	757	5	6	8	15449	12874	9656

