* The prevalence of abortion, stillbirth, premature birth, low birth weight, SGA and neonatal deaths was 10.1% in the same cohort recruited by Guangzhou Women's Center for 2012-2017.

Questionnaire and follow-up

We will obtain informed consent from participants. We will inform them of the main purpose of the study and the research process (Annex 1). We will emphasize that participation is completely voluntary. Refusal or withdrawal will not affect medical treatment and health care services at the Center. All information obtained by the research group will be strictly confidential and shall not be shared with any other third parties prior to obtaining consent from the participants. After enrolment, we will conduct a baseline survey with all participants, collect relevant medical history, information, and urine samples. The survey will be carried out by the research staff at the Center. The survey content will be built on the questionnaire that is developed by the birth cohort at the Center. We will obtain information on socio-demographic characteristics, chronic medical history, other acute conditions during the first trimester of pregnancy(diagnosis and treatment), number of pregnancies, prior history of previous caesarean section, history of recurrent miscarriage, prior

history of ectopic pregnancy, history of psychiatric illness (e.g., depression), smoking/drinking habits, and history of second-hand smoke exposure. We will add other questions to collect information about history of sexually transmitted diseases and gynecological diseases (such as cervical surgery), whether or not systemic or topical antibiotics were used within the past one month, drug use, sexual behaviors, sexual partner history both before and during pregnancy, history of falls during pregnancy, previous experience of domestic violence, etc. (Annex 2).

Participant recruitment and randomization

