prevention guidelines for sexually transmitted diseases, and final decision will be made by the physician and patient together. Physicians will ask patients to return to the women's center for test of cure and re-testing in one month and three months after treatment respectively. At each of these visits, we will collect urine samples for Chlamydia testing. Patients who still test positive will continue treatment until they test negative. Additionally, pregnant women who test positive for Chlamydia will also be suggested to bring Azithromycin home to treat their spouses. We will also caution them to avoid sexual activity during the treatment period (7-10 days starting from day of treatment). We will also provide consultation services for the participants to deal with intimate partner relationship under this circumstance.

For pregnant women enrolled in the control group, we will delay the urine sample collection and the test until after delivery, or in the event of adverse pregnancy outcomes. In the event of a positive test, the patients will be informed of the positive test results the same way as the intervention group. In the event of a positive test, physicians will be suggested to provide patients and their spouses with treatment identical to the intervention group. In the event of a negative test, there will be no need for treatment. Specific treatment options will be the same to the intervention group. Physicians will ask patients to return to the Center one month after treatment for test of cure. Endpoint of the study is defined as either the occurrence of an adverse pregnancy outcome or delivery of a newborn.

After delivery, all patients who tested positive will be informed of the risk of Chlamydia infection in neonates. About 1-week post-partum (including Caesarean newborns), neonatal conjunctival scrapings and nasopharyngeal/pharyngeal swabs will be collected. In addition, infants will be examined for neonatal conjunctivitis and / or pneumonia clinical symptoms (see details in secondary outcome). In the case of a confirmed diagnosis, treatment will be carried out.

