Urine Sample Collection Staff Training: Laboratories from Guangdong Dermatology Hospital will provide training to urine sample collectors and demonstrate how to properly collect and store urine samples. The total training time will be 2 hours.

Questionnaire data entry: The research team will use Epidata, a data input software, to manage the questionnaire data. Two data processors will be responsible for dual entry to reduce input errors.

Clinical Data Audit: Three clinicians from Guangzhou Women and Children Medical Center will be responsible for verifying the diagnosis and treatment plans of patients and their children according to the international classification of diseases and diagnostic criteria.

VIII. Annual Plan

Task/Year	1 st year	2 nd year	3 rd year	4 th year	5 th year
Study design, project propose and preparation					
Start pilot study to understand the disease prevalence among the target population					
Recruit participants\ baseline survey and collecting urine sample					
Randomization					
CT detection for intervention group					

patients and their partner CT treatment for intervention group					
primary report					
CT detection for control group					
patients and their partner CT treatment for control group					
Midterm report					
Follow up survey after delivery					
final report					
clinical data collecting					
Date input, management and analysis					
Manuscript writing and publishing					
Summary Report					

IX. References

4. N L. Sexually Transmitted Infections in Primary Care 2013 (RCGP/BASHH), 2013.

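### The stated 80% power is counted in infected women, but the primary outcome compares the randomised groups, where power is at best about 13% at 6% prevalence; an infected-only comparison would not be randomised

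*Combined protocol and SAP*

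**What the plan says.** All references are to the combined protocol and SAP.

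- **Sample size estimation.** The aim is to show a lower incidence of adverse outcomes in the intervention group than in the control group, with 80% power at two-sided 5%. The inputs are an odds ratio of 1.8 (infected versus uninfected women), a 10% risk, 6% prevalence and 2% loss. Each arm "should be approximately 7,725 for each group with an overall target sample size of 15,450". The table counts power in the number "of positive samples": 757 for 80% and 995 for 90%. It then converts these to totals at 5%, 6% and 8% prevalence.
- **Primary Outcome.** "Our primary outcome is the occurrence of adverse pregnancy-related outcomes between the two groups". There is no restriction to infected women.
- **Test timing.** Under Participant recruitment and randomization, the intervention group is tested at once, and "For the control group, urine samples will be collected and tested immediately after childbirth or in the event of an adverse pregnancy outcome". Intervention and Treatment repeats the delay: "we will delay the urine sample collection and the test until after delivery, or in the event of adverse pregnancy outcomes". Justifications of the control strategy describes the control condition as "free screening for chlamydia at delivery of the baby and linkage to care".
- **Urine at enrolment.** Questionnaire and follow-up says "we will conduct a baseline survey with all participants, collect relevant medical history, information, and urine samples". The Annual Plan has a recruitment row that includes "baseline survey and collecting urine sample".
- **Analysis set.** No section of the available text names it.

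**The concern.** The number of women follows from a comparison among positives, while the outcome is worded as a comparison of arms. About 94-95% of women in each arm are expected to be uninfected, and screening and treatment cannot change their risk. A contrast that is sizeable among positives is therefore heavily diluted across whole arms.

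The alternative is to compare positives. There, infection status is a baseline value in one arm and a post-randomisation value in the other. The control positives are the women found positive at the end of pregnancy. Infection can clear, be acquired, or be found and treated in usual care before then, and some women may miss the test.

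The plan thus leaves two analyses open. One is randomised but has little power. The other has about the stated power but is not protected by randomisation. A null result from the first would tell the reader little, and a result from the second could be reported as the trial's randomised finding.

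**Working it through.** **1. The plan's own figure.** Total = positives / prevalence / (1 - 0.02).

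- 757/0.05/0.98 = 15,449; 757/0.06/0.98 = 12,874; 757/0.08/0.98 = 9,656.
- The step from positives to total reproduces exactly. The 15,450 target is the 5% column, although the text states 6%.
- The 757 does not quite reproduce. An odds ratio of 1.8 on 10% gives odds of 1.8 x 0.1/0.9 = 0.2, so the risk is 0.2/1.2 = 16.67%. The pooled two-sided formula per arm is (1.96 x sqrt(2 x 0.1333 x 0.8667) + 0.842 x sqrt(0.1667 x 0.8333 + 0.1 x 0.9))^2 / 0.0667^2 = 407, or 814 positives in total. With 757 the power is 77%.

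**2. Positives expected with 15,450 women.** 15,450 x 0.98 x prevalence = 757, 908 and 1,211 at 5%, 6% and 8%. Power is 77%, 84% and 93%.

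**3. All randomised women.** There are 15,450 x 0.98 / 2 = about 7,570 per arm. Assume that treatment removes all the excess risk. Intervention risk is then 10%, and control risk is 10% + prevalence x 6.67 percentage points.

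At 6% prevalence:
- Control risk is 10.4%, a difference of 0.0040.
- Pooled standard error = sqrt(2 x 0.102 x 0.898 / 7,570) = 0.00492.
- Power = Φ((0.0040 - 1.96 x 0.00492)/0.00492) plus the far tail = Φ(-1.15) + Φ(-2.77) = 0.126 + 0.003 = about 0.13.

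| Prevalence | Control risk | Power, all excess removed | Power, half removed | Total for 80% power (2% loss, all excess removed) |
|---|---|---|---|---|
| 5% | 10.33% | 10% | 6% | about 263,000 |
| 6% | 10.40% | 13% | 7% | about 183,000 |
| 8% | 10.53% | 19% | 8% | about 104,000 |

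If 10% is read instead as the overall control-arm risk, best-case power is 10.3%, 12.6% and 18.5%.

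**4. Event rate.** The note to the sample size table gives 10.1% for a cohort composite that does not list premature rupture of membranes. The Primary Outcome section includes it, so the true rate may be higher. With an assumed uninfected risk of 20% and the odds ratio kept at 1.8, best-case power is 13%, 17% and 27% at the three prevalences. With 30% it is 15%, 19% and 30%.

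**5. Comparability of positives.** Suppose treatment has no effect. The odds of an event among control positives equal the true odds times P(found positive | event) / P(found positive | no event). Two illustrations on a 10% risk, with assumed inputs:
- 90% of infections are still detectable at an event test and 80% at delivery: ratio 0.9/0.8 = 1.125, apparent risk 11.1%.
- 20% of infected controls with an event go untested, with no clearance: ratio 0.80, apparent risk 8.2%.

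The bias can run either way. Within controls, timing differs by outcome mainly for early losses, because most other events are tested at birth, as non-events are.

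**The case against.** The strongest reply is that nothing in the plan commits to comparing positives. Both the sample size text and the Primary Outcome section speak of the two groups, and late testing of controls is deliberate and justified under Justifications of the control strategy. A reader might infer that the primary result is biased by test timing. The documents do not support that: a comparison of all randomised women does not use infection status. This part of the reply stands, and what remains is the power.

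A reader might also infer a bias of known direction among positives. That is not supported either. Persistence, new infection, timing of losses and missed tests are not given, and recruitment at any gestational age makes any single model a poor fit.

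The event rate is a fair challenge to the exact percentages, but the conclusion of low power survives it (step 4).

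The urine conflict could be loose wording. The two passages that delay control collection are specific and agree, the baseline sentence may attach all participants only to the survey, and the flow chart is not shown. That supports asking for clarification and nothing more.

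Finally, a reader might conclude that newborn sampling is restricted by maternal test status. Intervention and Treatment places the swabs directly after informing positive mothers but does not state a restriction, and neonatal symptoms are listed under Clinical Data Collection without one. Only the laboratory-confirmed neonatal outcomes could be affected.

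**Conclusion.** The concern holds in this form: the 80% belongs to a comparison that is either not the stated contrast or not protected by randomisation. For the stated contrast, best-case power is about 10-19% over 5-8% prevalence, and about 13-30% if the composite risk is 20-30%. It falls to about 6-8% at 10% risk if half the excess is removed. These figures rest on the plan's odds ratio being the causal effect of infection. For positives, power is near the stated level (77% at 5% prevalence, 84% at 6%), but as the plan is written the comparison is observational, with bias of unknown size and direction. The power arithmetic and the lack of randomised comparability are secure. No claim is made that the primary comparison is biased.

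**What to change.** 1. Name all randomised women as the primary analysis set.
2. Replace the 80% with the power for that set. State the assumed prevalence, the share of excess risk removed, and an event rate that matches the full composite in the Primary Outcome section.
3. Label any comparison of positives that relies on the control delivery or outcome test as non-randomised and supportive only. Report the share of controls tested, by event status.
4. Reconcile Questionnaire and follow-up and the Annual Plan with the two sections that delay control collection, so that it is clear whether controls give urine at enrolment.
5. State whether newborn swabs depend on maternal test status. If they do, give the laboratory-confirmed neonatal comparisons the same label.

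These are changes to text and reporting at almost no cost. The price is stating openly that the randomised comparison has low power.

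One addition is optional. If controls do give urine at enrolment, it could be stored and tested after the endpoint, so that infection is defined at baseline in both arms. On the plan's inputs that set has about 77% power at 5% prevalence and 84% at 6%. The cost is real: storage, a stability check (the urine section gives no long-term limit), an ethics amendment, and up to about 7,700 extra assays. Urine that is not collected or kept at enrolment cannot be recovered later, so the choice should be made before recruitment.
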